**Table 3 Schedule of Assessments (Double-blind treatment phase)\***

		Washout phase (1 week)		Double-blind treatment phase (6 weeks)					
		1	2	3	4	5	6		
Visit No.	-	1	-	2	3	4	5	6	
Study timeline a	-	Screening	Week -1	Day 1	Week 1	Week 2	Week 4	Week 6	
Visit window (Day)		-21 ~ -4	-7 ~ -3	-2 ~ 1	5 ~ 11	12 ~ 18	26 ~ 32	40 ~ 43	
Obtain informed consent	X								
Hospitalization b									
Patient demographics and medical history		X							
Inclusion/ Exclusion criteria assessments		X		X				X	
Randomization c				X					
Dispense study drug		X		X	X	X	X	X f	
Study treatment compliance				X	X	X	X	X	
PANSS		X		X	X	X	X	X g	
CGI-S		X		X	X	X	X	X g	
DIEPSS				X	X	X	X	X g	
C-SSRS				X	X	X	X	X g	
Skin irritation assessment				X	X	X	X	X	
Laboratory test d		X		X		X		X g	
Pregnancy test e		X						X	
12-lead ECG		X		X	X	X		X g	
Body weight		X		X	X	X	X	X	
Body temperature, blood pressure, pulse rate		X		X	X	X	X	X	
Adverse event monitoring									
Blood sampling for PK					X	X		X g	

a Day 1 is defined as the day of the initial application of the study drug in the double-blind treatment phase, and Day -1 is defined as the day before Day 1.

b All subjects will be hospitalized from screening until Day 14 (Visit 4). After Day 14 and completion of assessments at Visit 4, a subject who meets the criteria can be an outpatient.

c Subjects will be randomized after scheduled assessments at Visit 2 are completed.

d All blood samples will be collected under fasting conditions (at least 10 hours after the last meal).

e To be performed only in female subjects who are premenopausal and of childbearing potential.

f The study drug for the open-label treatment phase will be dispensed.

g Must be performed before the initial application of study drug in the open-label treatment phase.

\* If a subject discontinues the study drug during the washout phase, the subject will undergo the following safety assessments: study treatment compliance, skin irritation assessment, laboratory test, 12-lead ECG, body weight, body temperature, blood pressure, pulse rate, and adverse event monitoring at the discontinuation visit in Table 4 outside Japan or that in Table 5 in Japan.

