**Table 4 Schedule of Assessments for outside Japan (Open-label treatment phase)**

	Double-blind treatment phase	Open-label treatment phase (28 weeks)									Discontinuation	Follow-up phase (1-2 weeks)
Visit No.	6	101	102	103	104	105	106	107	108	109	Discontinuation visit	Follow-up visit
Timeline from the beginning of the open-label treatment phase a (Study timeline)	- (Week 6)	Open-Week 1 (Week 7)	Open-Week 2 (Week 8)	Open-Week 4 (Week 10)	Open-Week 8 (Week 14)	Open-Week 12 (Week 18)	Open-Week 16 (Week 22)	Open-Week 20 (Week 26)	Open-Week 24 (Week 30)	Open-Week 28 (Week 34)	-	-
Visit window in the open-label treatment phase (Day)	-	Open-5-11	Open-12-18	Open-26-32	Open-50-64	Open-78-92	Open-106-120	Open-134-148	Open-162-176	Open-190-204	At discontinuation +5 f	6-17 days after completion of treatment or discontinuation e
Hospitalization b	←-----											
Inclusion/ Exclusion criteria assessments	(X)											
Dispense study drug	(X)	X	X	X	X	X	X	X	X	X		
Study treatment compliance	(X)	X	X	X	X	X	X	X	X	X	X	
PANSS	(X)	X	X	X	X	X	X	X	X	X e	X e	
CGI-S	(X)	X	X	X	X	X	X	X	X	X e	X e	
DIEPSS	(X)	X	X	X	X	X	X	X	X	X e	X e	
C-SSRS	(X)	X	X	X	X	X	X	X	X	X e	X e	
Skin irritation assessment	(X)	X	X	X	X	X	X	X	X	X	X	
Laboratory test c	(X)			X		X		X		X e	X e	
Pregnancy test d	(X)									X	X	
12-lead ECG	(X)			X		X		X		X e	X e	
Body weight	(X)	X	X	X	X	X	X	X	X	X	X	
Body temperature, blood pressure, pulse rate	(X)	X	X	X	X	X	X	X	X	X	X	
Adverse event monitoring	←-----											
Blood sampling for PK	(X)									X e	X e	

- a Open-Day 1 is defined as the day of the initial application of the study drug in the open-label treatment phase.
- b All subjects can be inpatients or outpatients.
- c At Visit 109 and at the discontinuation visit, blood samples will be collected under fasting conditions (at least 10 hours after the last meal). At other visits, blood samples should be collected under fasting conditions (at least 10 hours after the last meal) whenever possible.
- d To be performed only in female subjects who are premenopausal and of childbearing potential.
- e Must be performed before the beginning of post-treatment with antipsychotics excluding the study drug.

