**Table 5 Schedule of Assessments for Japan (Open-label treatment phase)**

	Double-blind treatment phase	Open-label treatment phase (52 weeks)												Discontinuation	Follow-up phase (1-2 weeks)
Visit No.	6	101	102	103	104	105	106	107	108	109	110	111	112	Discontinuation visit	Follow-up visit
Timeline from the beginning of the open-label treatment phase a (Study timeline)	- (Week 6)	Open-Week 1 (Week 7)	Open-Week 2 (Week 8)	Open-Week 4 (Week 10)	Open-Week 8 (Week 14)	Open-Week 12 (Week 18)	Open-Week 16 (Week 22)	Open-Week 20 (Week 26)	Open-Week 24 (Week 30)	Open-Week 28 (Week 34)	Open-Week 36 (Week 42)	Open-Week 44 (Week 50)	Open-Week 52 (Week 58)	-	-
Visit window in the open-label treatment phase (Day)	-	Open-5-11	Open-12-18	Open-26-32	Open-50-64	Open-78-92	Open-106-120	Open-134-148	Open-162-176	Open-190-204	Open-239-267	Open-295-323	Open-351-379	At discontinuation +5 f	6-17 days after completion of treatment or discontinuation e
Hospitalization b	←----->														
Inclusion/ Exclusion criteria assessments	(X)														
Dispense study drug	(X)	X	X	X	X	X	X	X	X	X	X	X	X		
Study treatment compliance	(X)	X	X	X	X	X	X	X	X	X	X	X	X	X	
PANSS	(X)	X	X	X	X	X	X	X	X	X	X	X	X e	X e	
CGI-S	(X)	X	X	X	X	X	X	X	X	X	X	X	X e	X e	
DIEPSS	(X)	X	X	X	X	X	X	X	X	X	X	X	X e	X e	
C-SSRS	(X)	X	X	X	X	X	X	X	X	X	X	X	X e	X e	
Skin irritation assessment	(X)	X	X	X	X	X	X	X	X	X	X	X	X	X	
Laboratory test c	(X)			X		X		X		X	X	X	X e	X e	
Pregnancy test d	(X)												X	X	
12-lead ECG	(X)			X		X		X		X	X	X	X e	X e	
Body weight	(X)	X	X	X	X	X	X	X	X	X	X	X	X	X	
Body temperature, blood pressure, pulse rate	(X)	X	X	X	X	X	X	X	X	X	X	X	X	X	
Adverse event monitoring	←----->														
Blood sampling for PK	(X)									X			X e	X e	

- a Open-Day 1 is defined as the day of the initial application of the study drug in the open-label treatment phase.
- b All subjects can be inpatients or outpatients
- c At Visit 112 and at the discontinuation visit, blood samples will be collected under fasting conditions (at least 10 hours after the last meal). At other visits, Blood samples should be collected under fasting conditions (at least 10 hours after the last meal) whenever possible.
- d To be performed only in female subjects who are premenopausal and of childbearing potential.

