### 11.3.5 Clinical Laboratory Tests

Blood and urine samples will be collected for clinical laboratory tests. The Investigators will record the date of collection and whether or not the subject is under

fasting conditions (at least 10 hours after the last meal) in the CRFs. All clinical laboratory tests will be performed centrally.

The clinical laboratory tests required by the protocol are listed in Table 15. Detailed instructions regarding clinical laboratory procedures, sampling, shipping, and reporting can refer to the instructions manual provided by the Sponsor/CRO.

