### Guidance for Blood sample Collection

- From screening until the end of the double-blind treatment phase  
Blood samples will be collected under fasting conditions (at least 10 hours after the last meal).
- During the open-label treatment phase  
Blood samples will be collected under fasting conditions (at least 10 hours after the last meal) at the last visit (Visit 109 outside Japan or Visit 112 in Japan). At other visits, blood samples should be collected under fasting conditions, whenever possible.
- At the discontinuation visit  
Blood samples will be collected under fasting conditions (at least 10 hours after the last meal).

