7.7.5 Laboratory Evaluations

Data for the following hematology, blood chemistry, and urinalysis parameters received from the central laboratory will be listed and summarized by treatment group and visit including LOCF endpoints for the double-blind treatment phase using the safety population and for the DSP-5423P treatment period on the DSP-5423P dosed population. Observed values and changes from baseline will be summarized.

Statistical Analysis Plan

Version: 2

Study No. D4904020

Hematology	Blood Chemistry	Urinalysis
1. white blood cell count,	1. total protein,	1. glucose,
2. red blood cell count,	2. total bilirubin,	2. protein,
3. hemoglobin,	3. AST,	3. occult blood,
4. hematocrit,	4. ALT,	4. urobilinogen
5. platelet count,	5. ALP,	
6. neutrophils,	6. γ -GTP,	
7. eosinophils,	7. LDH,	
8. basophils,	8. total cholesterol,	
9. monocytes,	9. triglycerides,	
10. lymphocytes	10. BUN,	
	11. creatinine,	
	12. CK,	
	13. Na,	
	14. K,	
	15. Cl,	
	16. blood glucose,	
	17. HbA1c,	
	18. serum prolactin	

All laboratory data will be reported in conventional units. Out-of-reference-range values will be flagged as high (H) or low (L) in the listings.

For analysis purposes, values preceded by a “<” sign (i.e. those below the limits of quantification) will be set as missing. If values preceded by a “>” sign (i.e., those above the limits of quantification) are observed, handling will be discussed at BDRM. Note that these values with a “<” or “>” sign will be presented values as reported from the laboratory in the listing.

Mean change from baseline to Week 6 (LOCF) in selected parameters, which are serum prolactin concentration, glucose and HbA1c, will be analyzed using a nonparametric rank ANCOVA. For each pairwise comparison versus placebo, values of the change from baseline at LOCF endpoint and baseline values will be ranked. A linear regression will be conducted on the ranked change from baseline with ranked baseline value as independent variable to produce regression residuals. Using the values of the residuals as scores, Mantel-Haenszel row mean score tests will be produced for each DSP-5423P group versus placebo (Stokes, Davis, & Koch, 1995).

```
* compute the ranks of the response variable and covariate;
proc rank data = &ads out=ranks npuls12 ties=mean;
  var chg base;
  ranks rkchg rkbases;
```

Statistical Analysis Plan

Version: 2

Study No. D4904020

```
run;
* calculate the residuals from the linear regression;
proc glm data=ranks;
  model rkchg=rkbase;

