  output out=residual r=resid;
run;
* CMH mean score statistics are used to compare the groups;
proc freq data=residual;
  tables trt01p*resid / cmh2;
  ods output diffs=diff;
run;
```

Markedly Abnormal Post-Baseline Laboratory Values (MAPLV) for selected laboratory parameters can be found in Table 1. The criterion of MAPLV is satisfied if a value falls into the markedly abnormal range. Subjects will be represented in the count of a particular MAPLV if they have experienced that MAPLV at least once in the post-baseline (including unscheduled visits), regardless of baseline value, up to and including LOCF endpoints and repeat for each country. Only parameters with MAPLV throughout the study period per subject will be listed.

Table 1 Criteria for Markedly Abnormal Post-Baseline Laboratory Values

Hematology Parameter	Markedly Abnormal Range
Hemoglobin	Male: ≤ 11.5 g/dL
	Female: ≤ 9.5 g/dL
Hematocrit	Male: $\leq 37\%$
	Female: $\leq 32\%$
WBC	$\leq 2.8 \times 10^3/uL$
	$\geq 16 \times 10^3/uL$
Platelets	$\leq 75 \times 10^3/uL$
	$\geq 700 \times 10^3/uL$
Chemistry Parameter	Markedly Abnormal Range
ALT	$\geq 3 \times ULN$
AST	$\geq 3 \times ULN$
Alkaline Phosphatase	$\geq 1.5 \times ULN$
Na/Sodium	< 130 mEq/L
	> 150 mEq/L
K/Potassium	< 3 mEq/L
	> 5.5 mEq/L
Cl/Chloride	< 90 mEq/L
	> 115 mEq/L

Statistical Analysis Plan

Version: 2

Study No. D4904020

Blood Glucose (fasting)	< 50 mg/dL > 250 mg/dL
HbA1c	≥ 7.5%
Total Bilirubin	> 2 x ULN
Blood Urea Nitrogen	> 30 mg/dL
Creatinine	> 2.0 mg/dL
CK	> 3 x ULN
Serum Prolactin	≥ 5 x ULN
Triglycerides (fasting)	> 300 mg/dL
Total Cholesterol (fasting)	> 300 mg/dL

Box plot of observed value of the hematology and blood chemistry parameters will be provided for the double-blind treatment phase and the DSP-5423P treatment period by the treatment group and visit.

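### Open-label glucose and triglyceride changes are summarised against a fasting baseline without using the recorded fasting status, so a meal effect could be read as a drug or time effect

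*SAP*

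**What the plan says.** **Sampling rule up to Week 6.** Protocol Table 3 (footnote d) and the blood sampling guidance in Protocol 11.3.5 require a fast of at least 10 hours for every blood sample from screening to the end of the double-blind phase.

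**Sampling rule in open label.** Outside Japan, Protocol Table 4 makes fasting compulsory at Visit 109 and at discontinuation, then adds: "At other visits, blood samples should be collected under fasting conditions (at least 10 hours after the last meal) whenever possible". For Japan, Table 5 says "At Visit 112 and at the discontinuation visit, blood samples will be collected under fasting conditions", with the same softer rule elsewhere. The guidance in 11.3.5 repeats it: "At other visits, blood samples should be collected under fasting conditions, whenever possible".

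**What is recorded.** Under Protocol 11.3.5 investigators "record the date of collection and whether or not the subject is under" fasting conditions, in the CRF.

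**What is analysed.** SAP 7.7.5 covers both the double-blind phase and the DSP-5423P treatment period, by treatment group and visit including LOCF endpoints: "Observed values and changes from baseline will be summarized". Blood glucose and triglycerides are in the parameter list, and box plots are planned for all haematology and chemistry parameters. Neither the summaries nor the plots are filtered or split by fasting status. Fasting appears in 7.7.5 only as a row label in Table 1 (markedly abnormal values), for glucose, triglycerides and total cholesterol. The counting rule beside that table does not say that unfasted values are left out.

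**The concern.** A change from baseline is interpretable only if both samples are taken under the same conditions. Here the baseline must be fasting, while most later open-label samples need not be. After Week 6 every subject receives DSP-5423P, so no concurrent arm can separate a meal effect from an effect of drug or time.

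Long-term safety is a stated secondary objective, and glucose and triglycerides are part of the metabolic picture. Unfasted samples at intermediate visits could produce an apparent rise that disappears at the last visit, where fasting is compulsory again. The information needed to check this is already collected but has no planned use.

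**Working it through.** The plan states no figure for this point, so there is none to reproduce. The check compares the sampling rules with the analysis rule and then sizes the possible artefact.

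**Step 1: baselines.** SAP 6.3 takes the on-treatment baseline for the 40 and 80 mg groups from the screening or Day 1 visit. For the placebo group it is the last double-blind value on or before the first DSP-5423P application. Both fall under the compulsory fasting rule.

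**Step 2: scheduled open-label laboratory visits (Protocol Tables 4 and 5).**

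| | Laboratory visits | Fasting compulsory | Fasting encouraged only |
|---|---|---|---|
| Outside Japan | 103, 105, 107, 109 | 109 | 103, 105, 107: 3 of 4 |
| Japan | 103, 105, 107, 109, 110, 111, 112 | 112 | 103, 105, 107, 109, 110, 111: 6 of 7 |
| Either region, up to Visit 108 | 103, 105, 107 | none | 3 of 3 |

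The discontinuation visit is also compulsory-fasting in both regions.

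**Step 3: the submission summary.** SAP 7.9 limits this analysis to data up to Visit 108, which has no laboratory draw. For a subject still on treatment, the LOCF value at that cut therefore normally comes from Visit 107, where fasting is only encouraged. For a subject who stopped earlier, it normally comes from the discontinuation visit, where fasting is compulsory. SAP 6.3 also maps discontinuation samples into the same analysis visits as scheduled samples, so sampling conditions can differ within one visit by discontinuation status.

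**Step 4: size.** Let f be the share of unfasted samples at a visit and D the mean difference between an unfasted and a fasting value. With a fasting baseline:

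observed mean change = true mean change + f × D

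The spurious part is f × D. The documents give neither f nor D. The values below are assumptions, chosen only to show the range: f from 0 to 50%, D of 10 to 40 mg/dL for glucose and 20 to 100 mg/dL for triglycerides.

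| f | Glucose, f × D (mg/dL) | Triglycerides, f × D (mg/dL) |
|---|---|---|
| 0% | 0 | 0 |
| 5% | 0.05 × 10 = 0.5 to 0.05 × 40 = 2 | 0.05 × 20 = 1 to 0.05 × 100 = 5 |
| 20% | 0.20 × 10 = 2 to 0.20 × 40 = 8 | 0.20 × 20 = 4 to 0.20 × 100 = 20 |
| 50% | 0.50 × 10 = 5 to 0.50 × 40 = 20 | 0.50 × 20 = 10 to 0.50 × 100 = 50 |

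At the Visit 108 LOCF endpoint, the artefact is this product times the share of subjects whose last sample came from an optional-fasting visit.

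**The case against.** The strongest reply is that fasting remains the protocol's default at the intermediate visits. Unfasted samples may be few, and nothing in the documents shows that they are not. This stands: the plan permits a bias but does not establish one.

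Other parts of the reply also stand:

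- **Controlled comparison.** The rank ANCOVA for glucose in SAP 7.7.5 uses Week 6 (LOCF), where every sample must be fasting. It is untouched.
- **Final LOCF endpoint.** Compulsory fasting at the last and discontinuation visits largely protects it.
- **Unscheduled samples.** SAP 6.3 does not map open-label unscheduled samples to analysis visits, so the by-visit point concerns mapped samples, not every sample drawn.
- **Other evidence.** HbA1c is in the same panel and, on general knowledge rather than anything in the documents, does not depend on the last meal. It is a partial cross-check on glucose but none on triglycerides. Body weight and BMI are also summarised.
- **Markedly abnormal values.** The natural reading of the fasting labels in Table 1 is that only fasting values count. What is missing is a sentence that says so.

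A reader might infer that country results at Open-Week 28 are confounded, because Visit 109 is compulsory-fasting outside Japan and optional in Japan. The documents do not support this as a planned comparison. SAP 7.7.5 repeats only the markedly abnormal counts by country, and those run over all post-baseline visits. The pooled Open-Week 28 summary does mix the two sampling rules, but no laboratory summary by country is planned at that visit.

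The reply does not remove the mismatch at intermediate visits or at the LOCF endpoint of the Visit 108 summary.

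**Conclusion.** The point holds in a limited form. As written, SAP 7.7.5 combines fasting and possibly unfasted glucose and triglyceride values at the intermediate open-label visits, and compares them with fasting baselines in an uncontrolled period. The fasting status that would resolve this is recorded but not used. The exposed results are the by-visit levels, change scores and box plots, and the LOCF endpoint of the Visit 108 summary.

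The size is unknown. Under the stated assumptions with 5% to 50% unfasted, it runs from 0.5 to 20 mg/dL for glucose and from 1 to 50 mg/dL for triglycerides. It is zero if all subjects fast. The formula also assumes that the baseline samples were fasting, as the protocol requires.

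It would be tempting to say that the open-label changes are biased upward, or that change from baseline is the only metabolic evidence. The first needs an unfasted share that the documents do not give, and HbA1c and weight contradict the second. No efficacy result, hypothesis test or controlled safety comparison is affected. It is a worthwhile correction to a descriptive safety analysis.

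**What to change.** In SAP 7.7.5, for the DSP-5423P treatment period:

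1. Present glucose and triglyceride levels, change scores, box plots and LOCF for samples flagged as fasting in the CRF. Beside these, give either the all-sample summary or a split by fasting status.
2. Report the fasting n at each visit.
3. State that the markedly abnormal criteria for glucose, triglycerides and total cholesterol count fasting samples only.
4. Treat a missing flag as not confirmed fasting.
5. Show the flag in the laboratory listing. SAP 7.1 already plans to list all collected data, so this mainly makes the variable explicit.

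The cost is a short SAP paragraph, one filter on a variable already collected and some extra table columns. There is a statistical cost too. Fewer values remain at the optional-fasting visits, and the subjects who happen to fast may differ from visit to visit, which could create a trend of its own. That is why both versions should be shown side by side, not the fasting subset alone.

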6.3 Analysis visits, baseline, and post-baseline measures

All data will be organized and analyzed according to the scheduled timing as outlined in Table 4 to Table 6 Schedule of Assessments and according to the visit denoted in the CRFs. Unscheduled visits may be used if scheduled visits are not available, as specified below. The data collected at the discontinuation visit within 7 days from the final application of study drug will be mapped to the next scheduled visit of the actual discontinuation date, as specified below.

Follow to assign analysis visit;

1. Decide post-base line measures,
2. Assign scheduled visit denoted in the CRFs,
3. Assign CRF discontinuation visits,
4. Assign CRF unscheduled visits, when applicable.

A. Double-blind treatment phase

(i) Baseline analysis visit

Defined as the last non-missing data of CRF Screening or CRF Day 1 (Baseline) visit on or before Day 1. Unscheduled visits will not be used.

Statistical Analysis Plan

Version: 2

Study No. D4904020

(ii) Post-baseline data

Defined as the non-missing data on Day 1 through 7 days after the final application of study drug except for Screening and Day 1 (Baseline) visit. Data assessed on Day 1 and captured in the CRF visits of Week 1, discontinuation, and unscheduled visits will be considered as post-baseline data. Data assessed on Day 1 and captured in the CRF visits of Screening and Day 1 (Baseline) will NOT be considered as post-baseline data.

(iii) Post-baseline analysis visit

The post-baseline data will be mapped to post-baseline analysis visits, ie, Week 1, 2, 4, and 6 as follows:

- (1) CRF Week 1, 2, 4, and 6 will be mapped to the corresponding analysis visits, regardless of the actual day of assessment.
- (2) CRF discontinuation visits will be mapped to the earliest missing analysis visit based on the relative day of assessment as follows:

Assessments and tests	Relative Day	Analysis Visit
PANSS, CGI-S, DIEPSS, C-SSRS, Skin irritation assessment, Body weight, Vital signs	Day 1 to 11	Week 1, 2, 4, 6
	Day 12 to 25	Week 2, 4, 6
	Day 26 to 39	Week 4, 6
	Day 40 or later	Week 6
12-lead ECG, Pharmacokinetic	Day 1 to 11	Week 1, 2, 6
	Day 12 to 25	Week 2, 6
	Day 26 or later	Week 6
Laboratory test	Day 1 to 25	Week 2, 6
	Day 26 or later	Week 6

Note: non-missing analysis visits will not be replaced.

- (3) CRF unscheduled visits will be mapped to the earliest missing analysis visit based on the relative day of assessment as follows:

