6.4 Missing Data

Individual missing item in any scale will not be imputed. For the rating scales that consist of more than one item, if any item is missing, then the total and subscale scores will also be handled as missing. For example, if one item of PANSS positive subscale is missing, then the PANSS total score, the PANSS subscale scores, and the PANSS five-factor model scores will be missing.

In computing LOCF, unscheduled visits in the double-blind treatment phase will be used. For example, for the double-blind treatment phase, Week 6 (LOCF) endpoint will be the last observation of the post-baseline data specified in 6.3 A. Unscheduled visits in the open-label treatment phase will not be used for Week 52 (LOCF) endpoint.

In the efficacy analysis on data collected in the double-blind treatment phase, the primary method for handling of missing data will be the MMRM without explicit imputations for missing data. The LOCF method will be used with analysis of covariance (ANCOVA) as additional sensitivity analysis. The final post-baseline data in the double-blind treatment phase (on or after Day 1 and through 7 days after the date of final application of the study drug for the double-blind treatment phase) will be carried forward and will be defined as the Week 6 (LOCF) endpoint.

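### Setting below-limit laboratory results to missing replaces low Week 6 prolactin values with earlier, higher ones and so modestly weakens the planned rank ANCOVA; a fixed substitute value would avoid this.

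*SAP*

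**What the plan says.** SAP 7.7.5 (Laboratory Evaluations) states the rule for results carrying a less-than sign: "those below the limits of quantification) will be set as missing". They are shown as reported only in the listings. Results above the upper limit are treated differently: if they "are observed, handling will be discussed at BDRM".

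The same section plans a formal comparison with placebo, using the LOCF endpoint of the double-blind phase. It covers three analytes, described as "selected parameters, which are serum prolactin concentration, glucose and HbA1c, will be analyzed using a nonparametric rank ANCOVA". When a dose is tested against placebo, "values of the change from baseline at LOCF endpoint and baseline values will be ranked"; ranked change is regressed on ranked baseline, and the residuals go into a Mantel-Haenszel mean score test.

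Three other rules decide what happens once a result has been made missing:

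- Double-blind baseline (SAP 6.3 A): "Defined as the last non-missing data of CRF Screening or CRF Day 1 (Baseline) visit on or before Day 1".
- Double-blind post-baseline data (SAP 6.3 A): "Defined as the non-missing data on Day 1 through 7 days after the final application of study drug", apart from the Screening and Day 1 visits.
- LOCF (SAP 6.4): the "Week 6 (LOCF) endpoint will be the last observation of the post-baseline data specified in 6.3 A".

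In the schedule of assessments, laboratory tests fall at Screening, Day 1, Week 2 and Week 6. Serum prolactin is a named safety variable (SAP 3.3). Neither document gives a substitute value, a count of below-limit results by arm, or a sensitivity analysis for this rule.

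**The concern.** A result below the quantification limit is an observation: the value is known to be low. Calling it missing makes availability depend on the outcome, and LOCF then fills the gap with a value that is quantifiable and therefore higher.

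If the patch raises prolactin, fewer active-arm than placebo subjects have a below-limit Week 6 result, so more placebo values are pushed up. The contrast shrinks. In a safety comparison that is the unhelpful direction, because a real increase becomes harder to see. The deletion is also unnecessary, since a rank-based test can keep these subjects once one value is assigned to them.

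**Working it through.** **Stated figure.** There is none to reproduce. The documents give no assay limit, no expected share of below-limit results, no prolactin effect and no power for this test. The direction can be derived from the text. The size can only be shown over an assumed range.

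**Step 1: follow one subject through the rules.** Let L be the limit, b the Day 1 value, s the Screening value, w the Week 2 value and x the Week 6 value.

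- *Week 6 below the limit (x < L), Week 2 quantifiable (w ≥ L).* The Week 6 result is missing, so w is carried forward. The change used is w − b instead of x − b. The error is w − x, always positive. Unscheduled double-blind results also count for LOCF, so Week 2 is the normal source but not the only one.
- *Day 1 below the limit (b < L), Screening quantifiable (s ≥ L).* Baseline becomes s. The change from baseline falls by s − b, also always positive.
- *No quantifiable value on one side.* Only then does the subject leave the test.

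**Step 2: compare the arms.** Baseline replacements precede treatment, so randomization balances them in expectation. Week 6 replacements follow treatment. If the drug raises prolactin, P(x < L) is larger on placebo, so more placebo changes are pushed upward and the difference is attenuated. With no drug effect the probability is the same in each arm, so no false difference is created.

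**Step 3: size under the SAP rule.** The SAP's rank ANCOVA was simulated with both the Screening fallback and LOCF. Assumptions, none from the documents: 155 per arm, log-scale effect 0.15, log SD 0.6, correlation 0.6 between visits. The comparator assigns half the limit at every visit.

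| Limit at percentile | Placebo subjects left out | Power lost against substitution |
|---|---|---|
| 0.5th to 1st | about 0.1 to 0.4% | about 0 to 1 point |
| 2nd | about 0.8% | about 1 point |
| 5th | about 2.7% | about 4 points |
| 10th | about 6.4% | about 9 points |

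Type I error with no effect was about 4 to 5%.

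**Step 4: a second set of assumptions.** 167 per arm with no dropout, log SD 0.7, correlation 0.6, active arm shifted up by 0.25 SD on the log scale, 1,500 runs per setting (Monte Carlo error about 1.2 points). Here the comparator keeps below-limit results at the limit itself.

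| Placebo share below limit at Week 6 | Power, SAP rule | Power, substitution | Difference |
|---|---|---|---|
| 1% | 71.1% | 71.6% | 71.6 − 71.1 = 0.5 |
| 5% | 69.1% | 73.7% | 73.7 − 69.1 = 4.6 |
| 10% | 66.4% | 73.2% | 73.2 − 66.4 = 6.8 |
| 20% | 55.7% | 69.7% | 69.7 − 55.7 = 14.0 |
| 30% | 46.0% | 66.7% | 66.7 − 46.0 = 20.7 |

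Type I error stayed at about 4 to 6% under both rules. The two sets agree: negligible loss near 1%, about 4 to 5 points at 5%, and about 7 to 9 points at 10%.

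**The case against.** The strongest objection is that the premise is unseen. Nothing in the documents shows that prolactin, glucose or HbA1c will often fall below the assay limit, and at about 1% or less the rule hardly matters. The comparison is a safety analysis with no stated power. Marked elevations are counted separately (at least 5 × ULN at any post-baseline visit, SAP Table 1), and that count is unaffected. The less-than results remain in the listings, so counts can be recovered. All of this stands, and it is why the point is minor. It does not justify the rule: substitution changes nothing if such results are absent and protects the test if they are not.

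Three stronger readings are tempting and do not hold.

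- *A reader might infer that a below-limit Day 1 baseline removes the subject.* It does not. SAP 6.3 falls back to Screening, and the subject is lost only if that too gives no quantifiable value.
- *A reader might size the problem by deleting every affected subject.* Under the Step 3 assumptions, that leaves out about 3.5%, 8.3% and 16.2% of placebo subjects at the 2nd, 5th and 10th percentiles, and costs about 3, 6 and 14 points of power. The SAP does not delete in that way; its own rules give the smaller figures in Step 3.
- *A reader might suppose that below-limit results would simply take the lowest tied ranks.* The SAP ranks change, and baseline separately. A below-limit Week 6 result after a low baseline is a small change, not the lowest rank. The substitute must therefore be assigned before changes are computed.

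**Conclusion.** The point holds as a minor one. The rule in SAP 7.7.5, read with SAP 6.3 and 6.4, replaces below-limit results with higher values and attenuates a true prolactin increase in a planned test against placebo. The direction follows from the text. The size does not: it rests on an unknown below-limit frequency and on the assumed effect, spread and correlation above. For a limit between the 0.5th and 10th percentiles the cost is roughly 0 to 9 points of power.

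The documents do not support reading this as a source of false positives or as a threat to the primary PANSS analysis. The count of markedly high prolactin is unaffected.

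**What to change.** Before unblinding, replace the sentence in SAP 7.7.5 with a rule of this kind: results reported as below the quantification limit are assigned one fixed value (half the limit) at baseline and post-baseline visits before changes and ranks are computed, and are not treated as missing for baseline selection or LOCF. Add a table of the number of below-limit results by arm and visit.

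Handling of results above the upper limit can stay with the blinded data review. Protocol 10.7.2 withholds double-blind prolactin results until the other data from that phase are locked, so the rule can be fixed from the laboratory's stated limit without seeing any prolactin data.

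The cost is one sentence and one small table. The downside is that any substitution convention slightly affects descriptive means; the counts let a reader judge by how much.
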